6.1.2 ADMINISTRATION AND/OR DOSING

Dose of the behavioral intervention is captured by length, number and frequency of intervention contacts.

Length: The intervention has an active period (3 months) and a maintenance period (3 months) for a total of 6 months from baseline to final endpoint measure. The active period of 3 months was chosen to allow time for participants to learn the oral care techniques and then have time to engage in the new oral hygiene behaviors to impact plaque and gingival indexes. We determined the appropriate length in preliminary work done during in the R34 with internal pilot funded. The length of the study visit was refined during the pilot to take about 2 hours and occur in 15-minute increments to accommodate the various activities and roles of study staff, while minimizing burden on the participant and care partner. During the visit, both the participant and care partner alternate between joint intervention activities (done with both the participant and care partner) and individual activities. For example, while the hygienist is doing the oral hygiene evaluation on the participant, the care partner is engaged in the coaching session with the interventionist.

Number and Frequency: The intervention includes 3 home visits and 2 telephone contacts (for care partner coaching). The rationale for 3 home visits is to minimize burden on the participant and care partner while meeting study objectives of obtaining baseline measures, measures following the active period (3 months) and measures following the end of the maintenance period (6 months from baseline). The baseline and month 3 home visit serve also to provide for face-to-face intervention delivery during which the focus is on skill building.³⁰ The two phone contacts are equally spaced between baseline and 3 months to continue the intervention coaching with the care partner and participant. This timing allows use of the combination of face-to-face and telephone delivery which are found to be effective in prior research³¹ and provide for efficient use of participant and care partner's time.

6.2 FIDELITY

6.2.1 INTERVENTIONIST TRAINING AND TRACKING

We use the NIH Behavior Change Consortium's treatment fidelity model¹⁶ to ensure design fidelity, we developed the care partner intervention components to closely align with the study's guiding framework¹⁶ and we standardized the protocols to a specified dose in terms of number, frequency, and length of contact.

Hygienist Training

The hygienists will be trained on the key points that differentiate intervention activities for the three study groups, in particular, we will emphasize that the tailored care plan occurs only for Treatment Group 2. To ensure the fidelity of the hygienist delivered intervention components, a PI or designee will

be present at the home visits of the two dyads within the first five enrolled to evaluate fidelity to the protocol. Also, all encounters will be audio recorded digitally and will be checked on a random schedule by a PI or designee to assess adherence. The team members and PIs will discuss adherence results and problem-solve barriers to adherence with repeat of concepts and role-play as needed.

Interventionist Training

To ensure design fidelity, we developed the care partner intervention components to closely align with the study's guiding framework and we standardized the protocols to a specified dose in terms of number, frequency, and length of contact.

The interventionists are trained on the coaching modules separately from the other staff and do not interact with the Control group or Treatment Group 1, reducing potential for contamination. To ensure that interventions are delivered as intended, a PI or designee will be present at the home visits for two dyads within the first five enrolled to evaluate fidelity to the protocol, completing standardized checklists for adherence to protocol. Also, all encounters will be audio recorded digitally and will be evaluated on a random schedule by a PI or designee to assess adherence using the standardized checklist. The team members and PIs will discuss adherence results and problem-solve barriers to adherence with repeat of concepts and role-play as needed.

Study Coordinator Training

To further reduce potential for contamination, training for the study coordinator also will clearly differentiate intervention activities for the three groups; we will emphasize that the tailored care plan and Adaptive Leadership Behavior training occurs only for Treatment Group 2. To ensure the fidelity of coordinator to consenting and data collection procedures, a PI or designee will be present at the home visits for two dyads within the first five enrolled to evaluate fidelity, completing standardized checklists for adherence to protocol. Also, portions of all encounters will be audio recorded digitally and will be checked on a random schedule by a PI or designee to assess adherence using the standardized checklist. The team members and PIs will discuss adherence results and problem-solve barriers to adherence with repeat of concepts and role-play as needed.

Intervention Tracking:

Debriefing with study coordinators and the PIs will occur in weekly meetings. The PIs and coordinators from both sites will meet quarterly with the interventionist, and hygienist at each site. Our debriefing process involves a discussion of issues encountered, problem-solving among the team members, and assessment of threats to fidelity and consistency across settings and across time. To ensure that any actions taken during the study balance research integrity with practical issues, we use the TECH Tool (Simpson et al., 2013), an algorithm for evaluating challenges and solutions that preserve fidelity. One of the PIs will facilitate the discussion of areas for improvement and lessons learned, using a developmental intent and incorporating multiple sources of information such as other team members,

protocols or literature. Lessons learned will be documented in meeting minutes where they can be accessed for use in planning future interventions.

6.3 MEASURES TO MINIMIZE BIAS: RANDOMIZATION AND BLINDING

The study team plans to take numerous steps to ensure a rigorous, unbiased study. Prior to the first visit, the statistician will be blinded when randomizing participant and care partner to study groups.

The procedures for the study visits differ based on which arm of the study a participant is assigned; thus, the research staff is not blind to the participant's assigned group. The randomization group determines which research staff members attend the home visits. The Research staff who conduct the study visits with participants and care partners will be trained to adhere to study procedures and interventions appropriately based on group assignment. The interventionist does not attend the visits for the Control Group and Treatment Group 1, reducing risk of contamination through delivery of in-person coaching. The participants will be recruited from local clinics and the intervention will be conducted at each participant's home, so the chances of contamination between the Treatment groups and the Control group is small.

Blinded randomization assignments will be determined by the statistician at the beginning of the study using a block (by sex) random allocation algorithm generated *a priori* by the statistician assuring there will be equal allocation to arms by site. Because the interventionist does not attend study visits for participants in the Control Group and Treatment Group 1, randomization must be done prior to the first visit.

This is a three-group randomized trial [Treatment Group 1, Treatment Group 2 and the Control Group] using randomization blocks by site to ensure balance within this potential confounder. Each randomization block will be composed of two units male and female in each treatment arm by site and randomization error will be minimized by ensuring that an equal number of all of units are randomized to each group. As minorities are recruited, they will sequentially be assigned to each group. To assess for randomization balance, we will use chi-square tests to examine if there are any statistically significant differences between race, and site by the three groups.

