9.4.2 ANALYSIS OF THE PRIMARY ENDPOINT(S)

Details of the analysis of the primary endpoints will be provided in the SAP. A summary of the planned steps are provided here.

The first step will test whether the intervention is associated with differences across groups in the primary oral hygiene clinical outcomes. We will use linear mixed models for continuous outcomes (e.g., plaque index and gingival index) accounting for within-participant correlation over time. In addition to group, all models will be adjusted for site and time point and the interaction between group and time point – to assess whether group difference varied over time – as fixed effects; we will include a random effect for participants to handle within-participant clustering. Significant interaction between group and time point ($p < 0.05$) will provide statistical evidence for the efficacy of the intervention in improving oral health outcomes in Treatment Group 2 as compared to Treatment Group1 and the Control Group.

The subsequent steps will test the strength of the indirect effect of the intervention on oral hygiene clinical outcomes through mediators such as care partner factors and oral hygiene behavior outcomes. The following step will test the indirect effects are stronger than the direct intervention effects in Treatment Group 2 compared with Treatment Group 1 and the Control Group. The final step will test whether the impact of the intervention on oral hygiene clinical outcomes is sequentially mediated first by care partner's factors and then by oral hygiene behavioral outcomes.

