9.4.3 ANALYSIS OF THE SECONDARY ENDPOINT(S)

The secondary endpoints are oral hygiene behavioral outcomes.

We will test whether the intervention is associated with differences across groups in the oral hygiene behavioral outcomes. We will use linear mixed models for continuous and ordinal outcomes accounting for within-participant correlation over time. In addition to group, all models will be adjusted for site and time point and the interaction between group and time point – to assess whether group difference varied over time – as fixed effects – and include a random effect for participants to handle within-participant clustering. Significant interaction between group and time point ($p < 0.05$) will provide statistical evidence for the efficacy of the intervention in improving oral health outcomes in Treatment Group 2 as compared to Treatment Group1 and the Control Group. Similar to the approach taken with the primary endpoints, we will then test the strength of the indirect effects of intervention on oral hygiene behavioral outcomes through mediators.

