*Target accrual: 120 dyads

Study Design

This is a three parallel arm randomized controlled trial (RCT) to evaluate the effectiveness of a care partner-assisted intervention to improve oral hygiene in individuals (≥ 60 years) with mild dementia. Participant-care-partner dyads were randomized into 1 of 3 groups: Treatment Group 1 (**TG1**), Treatment Group 2 (**TG2**), and the Control Group (**CG**) stratified by site. **TG1** and **TG2** were given smart electronic toothbrushes. Only **TG2** will receive in-home and telephone coaching throughout the duration of the study and were instructed to record daily brushing habits. The coaching sessions included individualized instruction on oral hygiene technique, cueing strategy development, or oral hygiene monitoring and coaching. **TG1** and **CG** did not receive coaching sessions. While randomization occurred at the dyad level (participant-care partner), primary study outcomes will be assessed at the participant level. The study duration was 6 months, including a 3 month intervention phase, in which coaching and educational modules were delivered, followed by a 3 month maintenance phase in which no coaching or educational modules were presented to participants. Data was collected by the study team at three visits: baseline, 3-months (end of active intervention phase), and 6-months (end of three-month maintenance phase). The primary endpoint is oral hygiene (plaque index, gingival index) at 3 months, with a secondary endpoint of 6 months to explore maintenance of intervention effects.

Study Aims

Aim 1: Evaluate the effectiveness of a care partner-assisted intervention to improve oral hygiene and oral hygiene behaviors in individuals with mild dementia.

Hypothesis 1a: Compared to CG, both T1 and T2 will result in improved oral hygiene as measured by reduced plaque index, and reduced gingival index, at 3 months.

Hypothesis 1b: T2 will have higher improvement than T1, relative to CG, in oral hygiene as measured by a greater reduction in plaque index, and gingival index, at 3 months.

Aim 2: Assess changes in mediating factors/process outcomes, including communication between the dyads, oral health knowledge, and self-efficacy for both participants and care partners to understand mechanisms of the intervention.

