Hypothesis 2: The effects of the intervention on oral hygiene outcomes (i.e., plaque index and gingival index) will be mediated by oral care self-efficacy, leadership self-efficacy, use of behaviors cueing, leadership focused communication.

Measures**Primary outcomes:**

1) Plaque index: UNC Modified Green and Vermillion Oral Hygiene Index. Plaque was measured as 0 = No plaque, 1 = Plaque covers $<1/3$ tooth, 2 = Plaque covers $\geq 1/3$ but $<2/3$ tooth and 3 = Plaque covers $\geq 2/3$ tooth. *The proportion of sites with plaque deposits on at least less than 1/3 of crown will be calculated for each participant for use in analyses.*

2) Gingival Index: UNC Modified Loe and Silness Gingival Index. Gingival inflammation is classified as 0 = Normal gingiva, 1 = Mild inflammation, no bleeding on probing, 2 = Moderate inflammation, bleeding on probing, 3 = Severe inflammation, tendency to spontaneous bleeding. *The proportion of sites with at least some mild inflammation will be calculated for each participant for use in analyses.*

Secondary outcomes:

Participant oral hygiene behavioral outcomes, note for outcomes with both participant and care-partner report, care-partner report will be used for all statistical analyses. Participant data will be presented descriptively by arm and time.

1) Participants' frequency toothbrushing (reported by participants and care-partners).

Numeric scale ranging from 1-6. Data will be dichotomized into the following categories: less than twice a day or twice a day or more. Care-partner response will be used for analysis.

2) Participants' duration of toothbrushing (reported by dental hygienist).

Ordinal measure, consisting of 3 response types (< 1min; ≥ 1 min & < 2min; ≥ 2 min). Data will be treated as ordinal.

For sensitivity analysis we will dichotomize responses into the following categories: < 2 min vs. 2 min or more.

3) Participants' frequency of interdental cleaning (reported by participants and care-partners).

Ordinal scale ranging from 1-6. Data will be treated as ordinal. For sensitivity analysis we will dichotomize responses into the following categories: < once per day or once per day or more. Care-partner response will be used for analysis.

4) Participants' interproximal cleaning technique (reported by dental hygienist).

Categorical measure, consisting of 4 response types. Responses will be dichotomized into the following categories: less than optimal or interproximal surfaces cleaned using 'c' shape.

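### Protocol 6.3 blocks allocation by sex within site, but the SAP names only site and its model does not commit to sex: state the factors used and, if sex was blocked, add it (minor)

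*Combined protocol and SAP*

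**What the plan says.** Protocol 6.3 names sex twice as part of the allocation. The list is generated in advance "using a block (by sex) random allocation algorithm", and "Each randomization block will be composed of two units male and female in each treatment arm by site". The same section describes the design as "using randomization blocks by site to ensure balance within this potential confounder".

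The SAP's Study Design text describes randomisation of dyads to the two treatment groups "and the Control Group (CG) stratified by site". It does not mention sex.

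On the models, protocol 9.4.2 states for the primary endpoints: "In addition to group, all models will be adjusted for site and time point and the interaction between group and time point". Section 9.4.3 repeats this for the secondary endpoints. Section 9.4.1 leaves the key covariates to the SAP. The SAP's Aim 1 model contains site, group, time, group by time, a person-level random effect and an open term for participant covariates. The only covariates it names for that term are the baseline indices and baseline functional status. Sex appears in the SAP as a baseline characteristic of participant and care partner and in the demographic tables, not as a model term.

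**The concern.** A factor used to restrict the randomisation is normally carried into the analysis. Blocking balances it across arms, so the arm difference varies less from trial to trial than a model without the factor assumes. The reported standard error is then too large and the test somewhat conservative. The SAP follows this practice for site but not for sex.

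At stake are a little precision in a trial with 54 completers against a target of 120, and the reader's ability to check that the model matches the randomisation. The protocol and SAP do not give the same list of factors, and the open covariate term leaves the choice of sex to the analyst.

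**Working it through.** **Plan's own figure.** The documents give no sex effect, within-person correlation or sex split. The stated minimum of 107 subjects (protocol 9.2) does not enter this question.

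**Inputs.** From the documents: 60 dyads consented; completers 19 control, 18 Treatment Group 1, 17 Treatment Group 2. Assumed: two sites of equal size; half men (one-third as a check); a sex effect constant over time explaining a share r of outcome variance (5%, 10%, 20%); within-sex correlation ρ between baseline and follow-up of 0.3, 0.5 or 0.7; follow-up outcomes modelled with the baseline index as a covariate. With half men, r = 20% is a gap of 1.0 residual SD between the sexes: 0.25/(0.25 + 1) = 0.20.

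**Closed form (site left out for simplicity).** Total variance is 1.
- Sex in the model: residual variance (1 − r)(1 − ρ²).
- Sex omitted: the baseline–follow-up correlation becomes c = r + (1 − r)ρ, and the residual variance is 1 − c².
- SE ratio, omitted to adjusted: √[(1 − c²) / ((1 − r)(1 − ρ²))].

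At ρ = 0.5:
- r = 5%: c = 0.525; √(0.7244/0.7125) = 1.008
- r = 10%: c = 0.55; √(0.6975/0.675) = 1.017
- r = 20%: c = 0.60; √(0.64/0.60) = 1.033

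**Simulation.** Null trials, permuted blocks of 3 within site by sex, reduced to 19/18/17; 3-month outcome on group, site and baseline, with and without sex; 4,000 trials per setting. SE ratio for half men:

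| ρ | r = 0 | 5% | 10% | 20% |
|---|---|---|---|---|
| 0.3 | 0.999 | 1.013 | 1.026 | 1.054 |
| 0.5 | 0.999 | 1.007 | 1.015 | 1.031 |
| 0.7 | 0.999 | 1.003 | 1.007 | 1.016 |

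With one-third men the ratios move by at most 0.002, and at r = 0 they are 0.998. Type I error was 4.0–5.4% with sex omitted and 4.5–5.6% with sex included. The Monte Carlo standard error is √(0.05 × 0.95/4,000) = 0.34 points.

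**Secondary outcomes.** Brushing frequency is split in two ("Data will be dichotomized into the following categories: less than twice a day or twice a day or more") and goes into the same linear mixed model. At the 36% twice-daily prevalence quoted in protocol 2.1, with ρ = 0.5, the ratios are 1.008, 1.017 and 1.035.

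**Group-by-time test.** A sex effect that is constant over time cancels in within-person change. Random-intercept models on the 3- and 6-month rows gave a group-by-time SE ratio of 1.000 for a continuous outcome and at most 1.003 for a binary or ordinal one. The 3-month ratios were 1.008 (r = 5%) and 1.032 (r = 20%) for the continuous outcome.

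**If allocation was by site only.** At ρ = 0.5 the ratios for r = 0, 5%, 10%, 20% are 0.990, 0.998, 1.007, 1.024. Taking reciprocals, adding sex widens the SE by about 1.0% and 0.2% in the first two cases and narrows it by about 0.7% and 2.3% in the last two.

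**Degrees of freedom.** Intercept, two group terms, site and baseline use 5 of 54, leaving 49; sex leaves 48. The critical value goes from 2.0096 to 2.0106, a factor of 1.0005. Functional status, which the SAP also names, would take one more from each; none of these calculations includes it.

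**The case against.** The strongest reply is that the SAP text is the later account. It stands beside the May 2024 accrual table and says in the past tense that dyads were randomised with stratification by site, whereas protocol 6.3 is a plan. If sex was not used in the end, the SAP is complete and adding sex is a matter of choice. This stands, and it is why the addition should depend on the allocation records.

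It is also fair that the covariate list is open, so sex is not excluded, and that a short list is defensible with 54 completers. This stands in part: permitting a term is not pre-specifying it. Protocol 9.4.2 and 9.4.3 cannot be faulted, because 9.4.1 hands covariates to the SAP.

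Several stronger readings are tempting but not supported.
- A reader might infer bias or inflated type I error. Omitting a blocked factor works the other way.
- A reader might infer a seriously conservative test. A single-time-point simulation without the baseline index does give type I error of 4.1% for a 0.5 SD sex effect and 2.8% for 1.0 SD. The SAP model includes the baseline index, which already absorbs much of a stable sex effect; with it, simulated type I error did not fall below 4.0%.
- A reader might infer that whose sex was blocked is unknowable, since dyads are randomised. The protocol uses participant for the person with dementia, and the SAP covariate term is participant-specific, so participant sex is the natural reading. One word would confirm it.
- A reader might take "As minorities are recruited, they will sequentially be assigned to each group" to mean non-random rotation. The same section describes a list generated in advance, and nothing shows that a rotation was used.

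**Conclusion.** The point holds as a minor one. The protocol describes blocking by sex within site, the SAP's design text mentions site alone, and the SAP model does not commit to sex. If sex was blocked, the 3-month standard errors are too wide by about 0.7%, 1.5% and 3.1% for a sex share of 5%, 10% and 20% at correlation 0.5. Over correlations of 0.3 to 0.7 the range is 0.3% to 5.4%. The 6-month contrasts are affected in the same direction. There is no bias, and the group-by-time gate does not move materially.

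The sizes rest on an assumed sex effect constant over time, assumed correlations, sex split and equal sites, and on reading the SAP model as follow-up outcomes with baseline as a covariate. The 20% case, a full residual SD between men and women, is an extreme. Whether the term is called for by the design depends on allocation records that the documents do not contain.

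**What to change.** In the SAP's Study Design text, list every factor used in the allocation, taken from the records, and say that the sex concerned is the participant's (or the care partner's, if that is what formed the block).

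In the SAP's Aim 1 model, if the records confirm that sex was blocked, name that sex as a pre-specified fixed effect beside site for the primary and secondary outcomes. If allocation was by site alone, say so; sex is then optional. Protocol 9.4.2 and 9.4.3 need no edit. Settle this before database lock, by which 9.4.1 requires the SAP to be final. While the text is open, one sentence could state how the remark on sequential assignment of minorities relates to the advance list.

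The cost is a few sentences, no new data and one degree of freedom. If sex was blocked but explains nothing, the standard error widens by about 0.1–0.2%. If allocation was by site only and sex explains nothing, it widens by about 1.0%.
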